One-Week "Blinded" CGS Use As in the JDRF Artificial Pancreas Project, prior to randomization, each family will be given a "blinded" CGS device (glucose feedback disabled) to use for 7 days and to return to the clinic for downloading. A minimum prerequisite for randomization will be at least 96 hours of analyzable CGS data. In addition to providing valuable data, this will serve as a "run-in" period to screen out participants who cannot comply with basic requirements and enable them to withdraw if they find CGS use to be intolerable (6 of 451 JDRF participants did so). Blinded CGS use will recur at 3, 6 and 9 months. CGS data obtained from SC participants in this manner will be compared to comparable data obtained during CGS use by those in the CGS and CGS+BT groups. Periodic 7-day samples of CGS data will be randomly selected from these participants' downloaded CGS data from within the month prior to each quarterly clinic visit.

Hemoglobin A_{1c} and other medical variables Finger-stick blood samples will be obtained for central laboratory HbA_{1c} assays at Baseline and each 3 months. For eligibility verification and clinical use, HbA_{1c} will be measured on DCA-2000 analyzers (Bayer Diagnostics Inc.) at each site as usual.¹⁴⁶ Blood samples will be obtained at each quarterly visit and sent to the Baptist Medical Center lab in Jacksonville using the sample collection and shipping protocol that is currently used in the FMOD trial. Assays will be run on a Tosoh Analyzer using cation-exchange HPLC to separate hemoglobin fractions, including stable A_{1c}, by a buffer gradient of increasing ionic strength. Coefficients of variation range from 2-3%. Several studies have shown high correlations between HbA_{1c} measured by DCA-2000 versus central labs using such HPLC, but there is consistent bias in DCA-2000 results so that central lab measurement is needed.¹³² Other medical variables that will be obtained quarterly include Tanner Stage (breasts for females; genitalia for males; pubic hair for both), height, weight, Body Mass Index, linear growth velocity, and details of T1DM regimens.

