Hypoglycemia Diary As in our intensive therapy trial and DirecNet studies, parents will record youths' hypoglycemic episodes detailing the child's symptoms, date and time of the episode, results of SMBG tests, possible contributing factors, and the type of treatment. Hypoglycemia will be categorized by the Diabetes Nurse as Moderately Severe (requiring assistance from another person), or Severe (including seizures or loss of consciousness). Parents will report these events by phone, fax or e-mail to the clinic promptly after the episode. The nurse will interview the parent and patient to verify that the reported episode meets the criteria for severe hypoglycemia, to attempt to specify the cause of the event and to educate the family in an effort to prevent recurrence. The low frequency of severe or moderately severe hypoglycemia may impede treatment of these variables as primary outcomes in the statistical analyses. If so, we will analyze Kovatchev's measures of glycemic variability that are empirically validated indices of risk for severe hypoglycemia that confer the added analytic advantage of being continuous measures rather than discrete events.¹⁰²⁻¹¹³

Diabetes Self Management Profile This 24-item structured interview yields subscale scores for five domains of diabetes adherence (Exercise, Diet, Hypoglycemia, Glucose Testing and Insulin) and a total adherence score.^{83,147} Cronbach's alpha coefficient was .76 for the total score and inter-rater agreement was .94. The correlation between total scores of parents and adolescents was .72. Correlations with HbA_{1c} reported by

several research groups were consistently significant (range $-.25$ to $-.60$).^{14, 51, 147} Youths and parents will be interviewed separately by telephone by trained staff at Nemours-Jacksonville who are not associated with the diabetes clinical teams. Some interviewers will be native Spanish speakers. Interviews will be audio-recorded for later scoring and reliability checks. We will also record the frequency of SMBG testing and the extent of CGS use from computer downloads as additional indices of treatment adherence.

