5.7. Measurement schedule. In the measurement schedule below, "P" indicates collection of the measure from parent, "A" = from adolescents and "B" = from both parents and youths. All measures will be translated into Spanish and back-translated into English by native Spanish speakers. Participants may choose whether to complete the English or Spanish versions. Internal consistency and test-retest reliability will be calculated for each measure based upon data collected in the proposed study.

MEASUREMENT SCHEDULE

Measure	Study Visits (Months)				
	0	3	6	9	12
General Information Form (P)	•				
Glucose Meter memory downloads (A)	•	•	•	•	•
CGS Device downloads (A)	•	•	•	•	•
Measures of glycemic variability (A)	•	•	•	•	•
Hypoglycemia Diary (B)	•	•	•	•	•
HbA _{1c} (A)	•	•	•	•	•
7-Day Blinded CGS use (SC only)	•	•	•	•	•
Diabetes Self Management Profile (B)	•	•	•		•
Glucose Monitoring System Rating Scale (B)	•	•	•	•	•
BG Monitoring Communication Questionnaire	•	•	•	•	•
Hypoglycemia Fear Survey (B)	•	•	•	•	•
Diabetes Family Responsibility Questionnaire (B)	•	•	•	•	•
Wiebe Parental Involvement Interview (A)	•	•	•	•	•
Diabetes Responsibility & Conflict Scale (B)	•	•	•	•	•
PedsQL Diabetes Module (B)	•	•	•	•	•
Readiness to Change Questionnaire (B) (CGS+BT only)	•	•	•	•	•
Diabetes Problem Solving Interview (B)	•				

The only copyrighted instrument being administered is the PedsQL quality of life questionnaire, but Nemours owns a site license that permits free use and distribution for research purposes at all Nemours entities. Consequently, it will be possible to enable administration of the various measures via a secure internet connection using the Opinio software platform. This functionality will enable participants to complete questionnaires from anywhere that provides internet access at any time within the 2 week period immediately preceding each quarterly diabetes clinic visit. If participants are unable to accomplish this, the questionnaires will be available for hard-copy administration at clinic visits and they will be encouraged to do so during waiting times before and during their visits. This flexibility should enable participants to control the amount of time dedicated to study participation on clinic visit days.

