Hypothesis 3b: Improvements in HbA_{1C} during the 9-month Randomized Phase will be mediated by improved scores on the Diabetes Self-Management Profile, Diabetes Problem Solving Interview, Diabetes Responsibility and Conflict Scale, Wiebe Parental Supportive Involvement Interview, and Blood Glucose Monitoring Communication Questionnaire.

5.11. Other planned analyses. The proposed study will yield a rich data set, permitting many interesting analytic directions. Of special interest will be analyses of 1.) Maintenance (CGS and CGS+BT) and replication (SC) of treatment effects during the 3-month Continuation Phase; 2.) Determination of the frequency of CGS use that is associated with improvement in the various indices of glycemic control; 3.) Validation of mathematical models of CGS dynamics as predictors of the occurrence of severe hypoglycemia and HbA_{1C}; 4.) Evaluation of the temporal course of changes in glycemic variability and changes in HbA_{1C} during CGS use; 5.) Descriptive analyses of cost effectiveness as described in section 5.6; 6.) Between-group comparison using survival analysis of the time to first occurrence of severe or moderately severe hypoglycemia; and 7.) Prediction of changes in frequency of CGS use over time based on demographic and behavioral variables.

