5.12. Analytic procedures. *The randomized experimental design in this study will collect longitudinal data in a sequence of 5 time points at about 3-month intervals (Baseline, 3, 6, 9 and 12 months) from 3 treatment groups (SC, CGS, CGS+BT). Individual Growth Modeling¹⁶⁰⁻¹⁶⁴ will be applied to evaluate the treatment effects specified in the above hypotheses. The IGM approach, which also has been termed multilevel modeling, hierarchical linear modeling, or mixed effects modeling, is a particularly powerful and flexible approach for evaluating treatment effects within longitudinal data sets. The IGM approach has numerous advantages over traditional methods including 1) It compares the change of the outcome variable, such as HbA_{1C}, over time instead of comparing mean differences at specific time points; 2) It does not require that time points be equally spaced or data be collected at the same time at each time point for all participants. In fact, participants may have individually varying data collection over time during the study; 3) The covariates, such as site differences in this study, can be easily included in the model to adjust for these possible nuisance effects. 4) The covariance structure of the repeated outcome measures can be modeled and statistically compared to obtain more accurate estimates; and 5) It handles missing values flexibly—all available measurements of the outcome variable can be included in the analysis, thus increasing the power of the study.*

The basic individual growth model consists of two levels. The level-1 model is the estimation of the shape of individual change curves over time. The level-1 model for linear change is:

$$Y_{it} = \pi_{0i} + \pi_{1i} * Time + \varepsilon_{it}$$

where Y_{it} is the outcome variable for subject i assessed at time t , π_{0i} is the expected intercept for subject i , π_{1i} is the expected change rate (the slope) in the outcome for subject i , and ε_{it} is the within random error for subject i conditional on that subject's change parameters. In this study, the outcome variables will be the

youth's glycemic control, Kovatchev measures of glycemic variability derived from SMBG and CGS data, Diabetes Self-Management Profile, Diabetes Responsibility, and Conflict Scale, etc., that will be repeatedly measured over time. The variable Time in the level-1 model will be measured in months, starting from the baseline of the study to the time of data collection.

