Mediators are process variables that are affected by the treatment effect and are believed to have effects on the outcome. Mediator analysis will help us to understand the mechanisms why the treatment is effective. In mediator analysis we will determine whether the treatment effect is wholly or partial due to the mediators. Following Baron and Kenny,¹⁶⁶ traditional mediator analysis using cross-sectional data involves three regression equations, the outcome regressed on the treatment effect, the outcome regressed on both the treatment and the mediator, and the mediator regressed on the treatment. In the multi-level modeling framework, Krull & MacKinnon¹⁶³ introduced a detailed process of mediator analysis that has advantages over the methods used in the context of cross-sectional data. We will closely follow the approach recommended by Krull & MacKinnon¹⁶³ to examine the possible mediators proposed in Hypothesis 3b.

Specifically, in the IGM framework described above, HbA_{1c} will be the outcome in level-1 models and the treatment effect will be a dummy variable indicating treatment groups in level-2 models. Since all mediating variables in this study (the Diabetes Self-Management Profile, Diabetes Responsibility and Conflict Scale, Wiebe Parental Supportive Involvement Interview, and Blood Glucose Monitoring Communication Questionnaire) are within-subject variables measured repeatedly during the study, these mediators will be included in the level-1 model. Following Krull & MacKinnon,¹⁶³ the mediator analysis involves three stages of IGM: HbA_{1c} predicted by treatment alone, HbA_{1c} predicted by both treatment and the mediator, and the mediator predicted by the treatment alone. Combining the results from the three stages of IGM, we can determine if a candidate is a whole, partial, or non-mediator of the treatment effect in improving HbA_{1c}.

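### The mediation analysis for Hypothesis 3b sets no time order and states no indirect-effect interval, so a score that only reacts to HbA1c can be labelled a mediator

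*Combined protocol and SAP*

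**What the plan says.** Section 5.12, under Hypothesis 3b, says of the candidate scores that "these mediators will be included in the level-1 model", with HbA1c as the outcome. The level-1 equation in the same section defines its outcome term thus: it "is the outcome variable for subject i assessed at time t". No lag is attached to any predictor.

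The paragraph goes on: "the mediator analysis involves three stages of IGM". These are HbA1c on treatment, HbA1c on treatment plus the score, and the score on treatment. From the combined results, "we can determine if a candidate is a whole, partial, or non-mediator". No numerical criterion for the three labels is given. The section says the team will closely follow a cited multilevel mediation method.

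On timing, Section 5.7 lets families complete questionnaires "at any time within the 2 week period immediately preceding each quarterly diabetes clinic visit". For HbA1c, Section 5.5 says: "Finger-stick blood samples will be obtained for central laboratory HbA_{1c} assays at Baseline and each 3 months". The only planned analysis of temporal order is item 4 of Section 5.11, "Evaluation of the temporal course of changes in glycemic variability and changes in HbA_{1C} during CGS use". It does not cover the behavioral scores.

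**The concern.** Randomization protects the comparison of arms on HbA1c and on each score. It does not protect the path from score to HbA1c. If the score at a visit is regressed with HbA1c at that visit, a score that drives HbA1c and a score that responds to it both give a significant coefficient.

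The protocol itself expects the response direction for some of these scores. Sections 3.2 and 3.5 anticipate that glucose results may provoke parent-teen conflict. Section 5.5 includes the Blood Glucose Monitoring Communication Questionnaire partly to see how sensor data affect emotional reactions to glucose levels. Conflict and glucose-related affect are both Hypothesis 3b mediators.

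At stake is Aim 3. The report could name a behavioral mechanism that does not exist, and the behavioral manual is meant for dissemination. A categorical label also depends on which tests reach significance, so it can change with noise and sample size while the indirect effect stays the same.

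**Working it through.** **Inputs from the documents.** Section 5.13 gives baseline HbA1c 8.8% with SD 1.2%, SD 1.5% at the end, a 0.8% difference between CGS and CGS+BT at 12 months, and 45 per group. The correlation range comes from the adherence interview in Section 5.5: "several research groups were consistently significant (range $-.25$ to $-.60". Score stability is 0.70, the one-year retest value of the Blood Glucose Monitoring Communication Questionnaire.

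**Assumed, because not stated.** Two-sided alpha 0.05; within-person residual SD of HbA1c 0.45% (range 0.3 to 0.8); no intercept-slope covariance; linear change.

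**Calibration on the plan's own figures.** The plan gives no figure for mediation, so its growth-model power was used to calibrate.
- Effect size: 0.8/1.5 = 0.533, as stated.
- Slope difference: 0.8/12 = 0.0667 per month.
- Slope variance: (1.5² − 1.2²)/144 = 0.81/144 = 0.005625.
- Error variance of a five-visit slope: 0.45²/90 = 0.00225, where 90 is the sum of squared visit-time deviations (36 + 9 + 0 + 9 + 36).
- SE of the difference: √(0.005625 + 0.00225) × √(2/45) = 0.0887 × 0.2108 = 0.0187, so the ratio is 0.0667/0.0187 ≈ 3.56.
- Power is about 94.6%, against 94.5% stated. With residual SD 0.6 it is 89.7%, and with 0.8 it is 80.0%.

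**Simulation with no mediation.** The score at each visit is −r(HbA1c − 8.8)/1.35 + √(1 − r²)·e. Here 1.35 is the mean of 1.2 and 1.5, and e is 70% stable person effect and 30% visit noise. The score has no effect on HbA1c. There were 3,000 trials per setting, and the growth models had unstructured covariance.

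A mediator is declared if four conditions hold: treatment by time is significant for HbA1c, it is significant for the score, the score is significant as a level-1 predictor, and the treatment slope shrinks. The label is *whole* if that slope loses significance and *partial* otherwise.

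| Setting | r = 0.25 | r = 0.40 | r = 0.60 |
|---|---|---|---|
| 0.8% at month 12 (0.8 × 9/12 = 0.6% at month 9), visits 0 to 9 | 9.6% | 21.1% | 44.0% |
| Same effect, all five visits | 18.3% | 35.8% | 64.9% |
| 1.0% at month 9, visits 0 to 9 | 20.9% | 50.6% | 84.7% |

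The first row matches the phase named in Hypothesis 3b. The third uses the Section 5.8 projections, 8.4% − 7.4% = 1.0%. With r = 0 the rate is 0.2%.

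**What drives it.** In the first row the score is significant as a level-1 predictor in 93% to 100% of trials, so that stage screens out almost nothing. The limit is the power of the score-on-treatment stage (11.7%, 22.6%, 45.1%). The treatment slope shrinks by a median of about 3%, 9% and 23%, although the true indirect effect is zero.

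**Sensitivity to residual SD** (r = 0.60, first-row effect). At 0.3, 0.45, 0.6 and 0.8, declarations are 46.8%, 44.0%, 36.0% and 31.6%. The *whole* label rises from 1.3% to 4.7%, 9.0% and 12.5%.

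**Lagged model** (previous visit's score, adjusting for previous HbA1c, arm and time; same treatment conditions; first-row effect).

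| Score reacts to | Analysis | r = 0.25 | r = 0.40 | r = 0.60 |
|---|---|---|---|---|
| measured HbA1c | unlagged | 9.6% | 21.1% | 44.0% |
| measured HbA1c | lagged | 0.6% | 1.2% | 2.5% |
| error-free glycemia (2,000 trials) | unlagged | 2.8% | 13.8% | 45.8% |
| error-free glycemia (2,000 trials) | lagged | 2.0% | 8.5% | 35.8% |

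**The case against.** Several points on the other side stand.

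- **Same-visit pairing is not written.** A reader might infer that the plan prescribes it. The plan prescribes neither concurrency nor a lag. Same-visit is the natural reading of an unlagged level-1 predictor, so the defect is missing temporal order.
- **The cited method may supply an interval.** That cannot be checked here. What can be said is that the plan states none, while it does spell out its stages and its categorical conclusion.
- **False declaration is not the expected result.** A reader might infer that a reactive score would be declared a mediator. On the powering effect over nine months, non-declaration is the likelier outcome at every correlation tried. The highest nine-month figures need the 1.0% difference, which is not the effect the trial was powered on.
- **The correlations are borrowed.** The range of 0.25 to 0.60 belongs to the adherence interview. Section 5.5 gives no value for the affect scale beyond significance, and none with HbA1c for the conflict scale. The simulation also treats the whole correlation as reverse effect, which is a worst case.
- **Multiplicity adjustment is promised in Section 5.9, with no method named.** In a separate run of 800 trials per setting, Bonferroni over the four scores listed as repeatedly measured (0.05/4 = 0.0125) cut the rates from 13%, 25% and 49% to 4%, 10% and 28%. The problem shrinks but remains.
- **Lagging has a price.** With genuine mediators (assumed treatment shift of 0.5 to 0.8 score SD, and 0.3% to 0.6% HbA1c per score SD), a month-6-to-9 lagged rule detected 9% to 45% when the mediator acted within the quarter, against 57% to 96% for the concurrent rule. With a three-month delay the order reversed: 29% to 88% against 2% to 14%. The documents do not state the action time, so they do not support making the lagged analysis the sole rule.

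**Conclusion.** The concern holds in a limited form. Nothing in the mediation plan separates a cause of better HbA1c from a reaction to it, and the plan offers a label where an estimate is needed. Under the stated assumptions, a purely reactive score is declared a mediator, mostly a partial one, in roughly 10% to 44% of trials on the powering effect over months 0 to 9, and in about 21% to 85% if the difference is 1.0% at month 9. The percentages are illustrative. They rest on the assumed alpha, residual SD and decision rule, on one instrument's correlations, and on four complete visits. Multiplicity adjustment would lower them.

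A reader might also infer that lagging cures the problem. It does so only if scores react to measured HbA1c; if they react to underlying glycemia, the gain at r = 0.60 is from 45.8% to 35.8%. The point bears on how Aim 3 is interpreted. It does not touch the treatment comparisons of Aims 1 and 2, or safety.

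**What to change.** In Section 5.12, Hypothesis 3b:

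1. Replace the three labels with the indirect effect, as a product of coefficients, and a 95% interval from a bootstrap that resamples patients.
2. State the visit pairing. Describe unlagged results as associations, not mechanisms. An interval does not settle direction, since the treatment slope shrank in the simulations with no mediation at all.
3. Beside the unlagged analysis, add a lagged one: score at the previous visit predicting HbA1c at the current visit, adjusting for HbA1c at the previous visit and for baseline HbA1c and baseline score. Present it as a check on direction, and keep mechanism wording cautious even if the two agree.
4. Confirm whether the adherence interview is done at month 9. The Section 5.7 schedule as printed marks months 0, 3, 6 and 12 only, while Section 5.5 lists it among the quarterly measures. The printed table may be imperfect.

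The cost is analysis wording and modest extra code on data already planned. The lagged analysis has one fewer usable interval per patient and lower power if a mediator acts within a quarter, which is why it should accompany the unlagged analysis and not replace it.

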5.2. Participants. A sample of 150 youths with T1DM will be recruited from Nemours Children's Clinics (~50/center) in Wilmington, Delaware and in Orlando and Pensacola, Florida. Participants will not be recruited in Jacksonville because ongoing studies there would impede recruitment for this study. Nemours registrations show 914 current T1DM patients at the three sites who will be in the targeted age range (11 to <17 years old) at the start of enrollment. Of these, 518 patients (57%) have $HbA_{1C} \geq 7.5\%$, and this will probably increase as these patients age. The combined clinical populations at the three sites have been growing by about 300 T1DM patients annually, and so there should be over 550 eligible patients by the start date. The proposed sample size is justified in Section 5.13. With 35-45% recruitment rates in prior similar studies, and the likelihood that 15-20% of prospective youths are likely to be excluded based on the enrollment criteria, achievement of the recruitment goal requires that the study draw upon three clinics. Based on similar studies, we expect <10% attrition over the 12-months, yielding complete data on at least 135 youths. The parent or other caregiver who is most involved in each child's diabetes care will be required to participate, and other caregivers will be allowed to participate. Eligibility criteria were designed to enroll appropriate candidates for use of a CGS device who have recently achieved suboptimal HbA_{1C} . These criteria include:

- Age of child ≥ 11 years and < 17 years. This age range was chosen because families of adolescents often struggle with diabetes management. Youths ≥ 18 years old may be likely to leave home during the study.
- Duration of diabetes ≥ 2 years or ≥ 1 year with negligible stimulated c-peptide level, to exclude those with significant residual pancreatic insulin production.
- *Most recent $HbA_{1C} \geq 7.5\%$ and $\leq 10.0\%$ or mean HbA_{1C} over the prior 12 months within that same range.*
- *Youth has never used a CGS device for clinical management of diabetes.*
- Absence of any other medical conditions that, in the opinion of the attending endocrinologist, would impede completion of the study protocol.
- Youths may not be on daily glucocorticoid medications due to hyperglycemic effects of these agents.
- Intention to remain in the same region and to maintain diabetes care at the enrolling center for 12 months.

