- A 2-week follow-up visit with the diabetes nurse to download the CGS device and further education about responding to CGS data prospectively and retrospectively. Clinical insulin dose adjustment algorithms previously developed and validated in DirecNet studies will be taught to adolescents and parents. A JDRF website will soon be available that will offer additional teaching materials and supports designed for patients using CGS as a component of diabetes management.
- A 1-month follow-up visit with the diabetes nurse to review the family's use of the insulin adjustment algorithms and to evaluate the need for individual refinement of the algorithms.

- The diabetes nurse will be permitted to bring selected adolescents and parents in for interim clinic visits as needed for remedial education to ensure that the adolescent and parent have the requisite knowledge and skills required for deriving optimal benefit from use of the CGS.

Based on the DirecNet Navigator pilot study, we expect HbA_{1c} to decline by approximately 0.3 SD over 9 months to a mean value of about 8.4% for this group.

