Based upon effect sizes achieved in our studies with similar samples, we anticipate that the CGS+BT group will achieve and maintain a mean HbA_{1c} of about 7.4% for effect sizes of 1.2 SD relative to the SC group and 0.8 SD relative to the CGS group. The sampling plan is designed to achieve adequate statistical power to detect effects of this magnitude. A 0.8 SD treatment effect is clinically significant. In terms of glucose variability and risk for hypoglycemia (measured by the LBG1), a recent study of 40 days CGS use (Navigator), 20 days blinded followed by 20 days un-blinded, showed that the LBG1 was reduced by ~0.35 SD during the period of un-blinded use of CGS compared to the blinded use period.¹⁰⁹ We anticipate larger effects in our trial due to its longer duration and enrollment of a sample with more pronounced baseline glycemic variability.

5.9. Data Management and Statistical Analysis Plans. Prior to excusing a parent or youth after completion of any type of data collection, the researcher will ensure that missing items are completed and that errors are corrected. Measures will be recorded on scannable forms for scoring using the OpScan 4.0 optical scanner (NCS-Pearson, Inc., Minneapolis, MN). Data will be double-entered and cross-checked before final computer entry. Data files will be backed up nightly, password-protected and stored on a local area network. Participants will be assigned study ID numbers that will be used rather than names to label completed questionnaires, paper records, etc. All raw data obtained during the project will be stored in locked file cabinets without names recorded on these items. The researchers will maintain a list of ID numbers paired with participants' names and will keep this list in a password-protected computer file separately from other data. Signed informed consent forms, which will contain participants' names, will also be stored separately in locked cabinets. Error checking routines will be created as part of the database application. Weekly reports will be generated for the purpose of monitoring the accrual patterns and for the completeness of data.

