5.13. Sample size and statistical power. Power analysis and sample size estimation were based on projected treatment effects on HbA_{1c}, the primary outcome measure, as shown in the figure below. To estimate sample sizes needed in the three groups for sufficient statistical power, a Monte Carlo simulation study was conducted using MPlus (Version 5).¹⁶⁴ The Monte Carlo procedure is the most common and the preferred methodology to estimate sample size in Individual Growth Modeling.¹⁶⁷⁻¹⁶⁸ In a Monte Carlo study, random samples are generated repeatedly using the known population parameters with a specified sample size. The percentage of simulated samples that have reached significance on the parameters is the estimated power of the study. Thus, the required sample size can be determined accurately by varying sample sizes in a series of simulations. MPlus provides extensive facilities for conducting Monte Carlo studies on IGM. Our simulation study followed the procedures recommended by Muthen & Muthen,^{164, 168} including generating missing values to reflect expected attrition and the pattern of missing data in the proposed study. The primary contrast of interest in this study is change in HbA_{1c} relative to baseline values among adolescents in the SC,

CGS, and CGS+BT groups. Based on the mean HbA_{1c} obtained in several prior trials at Nemours Children's Clinic in Jacksonville and the stated enrollment criteria, we expect that the baseline mean and standard

deviation values will be approximately $8.8\% \pm 1.2\%$. The standard deviation of HbA_{1c} will increase gradually with each measure spaced about 3 months. At the end of 12 months, we expect a 0.8% difference in HbA_{1c} between the CGS and CGS+BT groups. Assuming a standard deviation of approximately 1.5% at the end of the study, the effect size will be 0.533, a moderate effect size as defined by Cohen¹⁶⁹ that is clearly clinically significant. Based on the retention rates in our NIH-funded randomized trials, we anticipate an attrition rate <10% during the 1-year study. Therefore, enrollment of 150 patients (50 per group) should result in at least 135 (45 per group) at the end of the 9-month randomization phase of the study. We anticipate that about 120 participants (40 per group) will complete the 3-month Continuation Phase of the study.

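### Hypothesis 1 covers the 9-month Randomized Phase, but its HbA1c model and stated power run to month 12, when Standard Care youths may use CGS; the sample-size inputs also disagree

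*Combined protocol and SAP*

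**What the plan says.** **Window.** Section 5.10, repeated in 5.12, states Hypothesis 1 as greater improvement with CGS+BT than with SC or CGS over the 9-month Randomized Phase. The HbA1c model in 5.12 then takes all measures from baseline to end of study, five per complete participant. It compares CGS+BT with CGS, CGS+BT with SC, and CGS with SC. The simulation in 5.13 uses the same five visits (0, 3, 6, 9 and 12 months) and reports 94.5% power for CGS+BT vs CGS. For SC vs CGS it reports above 80%. Section 5.1 offers the CGS regimen to all groups in months 9 to 12 and expects CGS benefits to be replicated in SC youths who choose it. Section 5.11 lists maintenance and replication in that phase as separate analyses.

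**Attrition.** Section 5.2: "we expect <10% attrition over the 12-months, yielding complete data on at least 135 youths". Section 5.13: "we anticipate an attrition rate <10% during the 1-year study". Section 5.13 then places the 135 at month 9 and adds: "We anticipate that about 120 participants (40 per group) will complete the 3-month Continuation Phase of the study".

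**Effect.** Section 5.8 expects CGS to "decline by approximately 0.3 SD over 9 months to a mean value of about 8.4% for this group". For CGS+BT it says "we anticipate that the CGS+BT group will achieve and maintain a mean HbA_{1c} of about 7.4" percent, with "effect sizes of 1.2 SD relative to the SC group and 0.8 SD relative to the CGS group", and adds: "The sampling plan is designed to achieve adequate statistical power to detect effects of this magnitude". Section 5.13 instead says: "At the end of 12 months, we expect a 0.8% difference in HbA_{1c} between the CGS and CGS+BT groups". With an SD of 1.5 this is 0.533 SD.

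**The concern.** The model that tests Hypothesis 1 does not match the period that Hypothesis 1 names. Followed literally, 5.12 fits one slope through nine months of randomized contrast and three months in which controls may use the device under test. If SC youths take up CGS and benefit, as 5.1 anticipates, the slope is pulled toward no difference in both SC contrasts: CGS+BT vs SC, which Hypothesis 1 names, and SC vs CGS, which 5.12 and 5.13 add. If the window stays unsettled, four or five visits could be used once the data are in hand, and the SC results would depend on that choice.

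The attrition and effect statements are a lesser matter. They are the written basis for 150 patients, and they disagree.

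**Working it through.** **Inputs from the documents.** Visits at 0, 3, 6, 9 and 12 months; 50 per group; SD 1.2 at baseline and about 1.5 at the end; 0.8 points at month 12 for CGS+BT vs CGS (5.13). Expected means for the Randomized Phase are about 9.0 (SC), 8.4 (CGS) and 7.4 (CGS+BT) (5.8).

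**Inputs not stated, hence assumed.** Two-sided alpha 0.05. A random-intercept, random-slope model with residual variance set so that the five-visit design returns 94.5%. Four loss patterns behind that figure: none; 10% evenly; 10% by month 9 and 20% by month 12; 20% evenly. Intercept-slope covariance from -0.015 to 0.025.

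**1. The plan's own figures.** 0.8/1.5 = 0.533 is correct. The 94.5% is attainable (for example, zero covariance, 10% even loss, residual variance about 0.23) but cannot be verified without the missing inputs.

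**2. Effect of month 12 on the slope.** With complete data, the fitted slope of the group difference d is

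(-6·d0 - 3·d3 + 0·d6 + 3·d9 + 6·d12)/90, where 90 = 36 + 9 + 0 + 9 + 36.

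If the difference grows in a straight line to D at month 9 (so d3 = D/3), the 9-month equivalent is 9 × slope = 0.2·D + 0.6·d12. If the line continues (d12 = 4D/3), this returns D. Otherwise:

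| Contrast | D at month 9 | d12 | Estimated 9-month difference |
|---|---|---|---|
| SC vs CGS | 9.0 - 8.4 = 0.6 | 0.6 | 0.12 + 0.36 = 0.48 |
| SC vs CGS | 0.6 | 0.3 | 0.12 + 0.18 = 0.30 |
| SC vs CGS | 0.6 | 0 | 0.12 + 0 = 0.12 |
| CGS+BT vs SC | 9.0 - 7.4 = 1.6 | 1.6 | 0.32 + 0.96 = 1.28 |
| CGS+BT vs SC | 1.6 | 8.4 - 7.4 = 1.0 (SC reaches the CGS mean) | 0.32 + 0.60 = 0.92 |

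With 10% even loss the three SC vs CGS values become about 0.48, 0.31 and 0.14. A four-visit model returns D in every row.

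**3. Attrition.** 1 - 135/150 = 10% at month 9; 1 - 120/150 = 20% at month 12. If the 94.5% allowed for 10% even loss, 20% by month 12 gives 93.6% at zero covariance (93.2 to 94.2% over all covariances). If it assumed no loss, the result is about 92%, but 5.13 says that missing values were simulated.

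**4. Effect.** 8.4 - 7.4 = 1.0 point, which is 1.0/1.2 = 0.83 SD or 1.0/1.5 = 0.67 SD. Neither equals 0.533 SD.

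**5. The two stated powers.** 94.5% corresponds to a standardized difference of 1.960 + 1.598 = 3.558. With equal variance, N and loss, 0.6 points gives 3.558 × 0.6/0.8 = 2.669, and 2.669 - 1.960 = 0.709, a power of about 76%. The two figures can agree if the loss differs: with information from 40 per group for the first and 45 for the second, 2.669 × √(45/40) - 1.960 = 0.870, or 80.8%.

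**6. Nine-month power, CGS+BT vs CGS (four visits, 10% loss).**

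| Difference at month 9 | Zero covariance | All covariances |
|---|---|---|
| 0.6 (the 5.13 slope: 0.8 × 9/12) | 84-90% | 71-95% |
| 0.8 | 97.5-99% | 92-99.8% |
| 1.0 (the 5.8 means) | 99.8% or more | 98.8% or more |

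**The case against.** Several points on the other side stand.

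- The simulation matches the planned model: both use five visits. The mismatch is between those two and the wording of the hypothesis, so it belongs to the analysis plan and is not an arithmetic error in 5.13.
- Section 5.13 does state the effect and month behind the 94.5%. Only the loss pattern, alpha and variance inputs are missing. The figure of projected effects that it cites is not in the text available here and may explain the path from the 9-month means to 0.8 points at month 12.
- A narrowing after month 9 could reconcile 1.0 with 0.8 points, and 5.1 allows that CGS+BT gains may deteriorate. But no narrowing is stated, and 5.8 says the CGS+BT mean will be maintained.
- The 20% loss is derived, and the Continuation Phase is only offered, so some of it may be opting out. Sections 5.2 and 5.13 nevertheless both apply under 10% to the full year.
- Section 5.12 may select a quadratic shape, which could reduce the dilution. The shape is chosen by AIC and BIC, so this is not assured.

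A reader might go further and infer that power collapses. In the calibrated linear model with 10% even loss, five-visit power for SC vs CGS is 42-49% if the 0.6 halves by month 12 and 11-15% if it closes. The documents do not support reading these as the trial's power. Hypothesis 1 does not name that contrast, uptake and benefit among SC youths are unknown, and the same model gives about 76% where the plan reports above 80%.

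**Conclusion.** The main point holds: the Hypothesis 1 HbA1c model includes a period outside its hypothesis, in which SC youths may use CGS. Dilution of the SC contrasts depends on uptake, benefit and the fitted shape. With a linear slope and 10% loss it takes a 0.6-point SC vs CGS difference to between about 0.48 and 0.14.

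The points in 5.13 are matters of consistency. The attrition conflict moves power by about 1 point if the 94.5% allowed for 10% loss. The effect conflict runs in the conservative direction. No 9-month power is given, and the two stated powers must rest on different inputs that are not reported.

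It would be wrong to infer that 150 is too few, or that 94.5% or above 80% is incorrect. At zero covariance, 9-month power for CGS+BT vs CGS stays at 84% or more even at 0.6 points; it falls below 80% only at 0.6 points under some of the larger positive covariances. All power figures here rest on the assumed alpha and the calibration to 94.5%.

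**What to change.** - In 5.12, restrict the Hypothesis 1 HbA1c model to baseline, 3, 6 and 9 months for all contrasts, and at minimum for both SC contrasts. Leave month 12 to the maintenance and replication analyses in 5.11. If 12 months is kept for CGS+BT vs CGS, say so in Hypothesis 1 and state the expected course after month 9.
- Re-run the existing simulation once on that window, with one difference per contrast (points, SD and month) and one loss figure per visit.
- Restate the powers with alpha, sidedness, visits, variance components and missing-data pattern, using the re-run's figures and not those above.
- Align 5.2, 5.8, 5.12 and 5.13.

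The cost is one simulation run, text edits and a real change to the primary model: month 12 no longer adds to the Hypothesis 1 slope. A stated power may fall, to about 84-90% for CGS+BT vs CGS if the month-9 difference is 0.6 points, or stay at 97% and above if it is 0.8 (zero covariance). No patients, visits or data are added.
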